6.3.3 Overall Eczema Area and Severity Index Score

Overall Eczema Area and Severity Index (EASI) score is the sum of the scores for 4 body regions (face, neck, and head; upper limbs; trunk; and lower limbs). The score for each region will be calculated as shown in Table 6.3-1.

Body region	Calculation of the score for each region
Face, neck, and head	$(E+I+Ex+L) \times \text{score of affected BSA} \times 0.1$ ($\times 0.2$ for children aged 2-7 years old)
Upper limbs	$(E+I+Ex+L) \times \text{score of affected BSA} \times 0.2$
Trunk	$(E+I+Ex+L) \times \text{score of affected BSA} \times 0.3$
Lower limbs	$(E+I+Ex+L) \times \text{score of affected BSA} \times 0.4$ ($\times 0.3$ for children aged 2-7 years old)

- E = severity score of erythema; I = severity score of infiltration/papules; Ex = severity score of excoriation; L = severity score of lichenification
- Severity score: clear = 0; slight = 0.5; mild = 1; mild-moderate = 1.5; moderate = 2; severe = 2.5; very severe = 3
- Score of affected BSA (for each region): clear = 0; 1% to 9% = 1; 10% to 29% = 2; 30% to 49% = 3; 50% to 69% = 4; 70% to 89% = 5; 90% to 100% = 6

6.3.4 EASI Symptom Score

Each EASI symptom score (erythema, infiltration/papules, excoriation, and lichenification) will be determined as the sum of the severity scores (Body Regions Scores) for 4 regions (face, neck, and head; upper limbs; trunk; and lower limbs) (The scores of affected BSA or multipliers will not be used in the calculation).

6.4 Study Week Windows

The definitions of timepoints for analysis are described in Table 6.4-1 and Table 6.4-2. Timepoints, including unscheduled visits and visit at discontinuation, will be determined based on the number of days from the start of IMP administration. However, for Verbal Rating Scale (VRS), the timepoint will be determined based on the amount of time that has elapsed from the start of IMP administration. For efficacy variables, the data obtained between the day of the start of IMP administration and 7 days after the last IMP administration will be used in analyses. If multiple data exist within the allowable window of the timepoint, the data obtained last will be used for analyses. Data for the Last Visit will be defined as the last data obtained between the day of the start of IMP administration and 7 days after the last IMP administration (including data obtained at discontinuation) for efficacy variables or as the last data obtained after the start of the IMP administration for safety variables.

In analyses, baseline data will be defined as data obtained on the day or at the date and time before and nearest to the start of IMP administration, including the screening data.

Table 6.4-1 Timepoints and Allowable Windows for Efficacy Variables (Except VRS) and Safety Variables				
Timepoint	Study Day	Allowable Window (Days After the Start of IMP Administration)		
Week 1	8	1	-	10
Week 2	15	11	-	21
Week 4	29	22	-	43

Table 6.4-2 Timepoints and Allowable Windows for VRS			
Timepoint	Allowable Window (Hours After the Start of IMP Administration)		
Hour 4	1	-	< 6
Hour 8	6	-	< 10
Hour 12	10	-	< 18
Hour 24	18	-	< 30
Hour 36	30	-	< 42
Hour 48	42	-	< 54
Hour 60	54	-	< 66
Hour 72	66	-	< 78
Hour 84	78	-	< 90
Hour 96	90	-	< 102
Hour 108	102	-	< 114
Hour 120	114	-	< 126
Hour 132	126	-	< 138
Hour 144	138	-	< 150
Hour 156	150	-	< 162
Hour 168	162	-	< 174

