#### **3.7.1.4 Allocation of Investigational Medicinal Products to Subjects**

The investigator or subinvestigator will enter the necessary information for subject's eligibility in the IWRS. On the day of the baseline examination, the subjects confirmed to be registered in the IWRS will be allocated to the 0.3% OPA-15406 group, the 1% OPA-15406 group, or the vehicle group. The investigator or subinvestigator will confirm the allocation result and the drug code of IMP to be prescribed for 2 weeks on the IWRS screen displaying the registration result and prescribe the IMP. The weight of the dispensed IMP will be measured (to one decimal place in unit of gram). (Hereinafter, when the weight of IMP is measured, it will be measured to one decimal place in the same manner.) After completion of all evaluations on the day of baseline examination, the first application of IMP will be given at the trial site, and date and time of the application will be recorded. The subjects will be instructed to visit the trial site without morning IMP administration on the day of the next visit.

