#### **3.7.1.5 Between the Day of Baseline Examination and the Day of Week 1 Examination**

The investigator or subinvestigator will instruct the subject to evaluate the following item at  $4 \pm 2$  hours,  $8 \pm 2$  hours (if possible),  $12 \pm 2$  hours (if possible) after the first IMP administration on the day of baseline examination, and then twice daily from the next day (before IMP administration in the morning and at night) up to the morning of Week 1 examination (before administration) (up to the morning of Day 7 at the latest).

- VRS for pruritus (only for 7 - 14 years of age)

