10.1.3 Change From Baseline in Visual Analogue Scale for Pruritus

The change from baseline in visual analogue scale (VAS) for pruritus will be analyzed in the same manner as that in the overall EASI score or each EASI symptom score.

10.1.4 Change From Baseline in VRS for Pruritus up to Day 7

The change from baseline in VRS score for pruritus up to Day 7 will be analyzed in the same manner as that in overall EASI score or each EASI symptom score. Data will be collected at baseline, 4, 8, and 12 hours after the start of administration, 1 day after the start of administration (morning and night), and thereafter in the same manner up to Day 7 (morning). The same analysis will be performed by the time zone of assessment (morning or evening). Morning or evening will be determined based on the time label entered in the case report form (CRF), not using the timepoints defined in Table 6.4-2, except the baseline, which is irrespective of the time zone of assessment. Data will be collected at baseline, and the timepoints specified above on Day 1 to Day 7.

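### SAP Table 6.4-2 bins the itch VRS diary by hours since first application, so a start more than 6 h after a child's usual morning reading shifts diary mornings and nights to other timepoints and leaves Hour 168 empty

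*SAP*

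**What the plan says.** Protocol 3.7.1.5 has children aged 7-14 rate itch about 4, 8 and 12 h after the first application (the last two if possible), "then twice daily from the next day (before IMP administration in the morning and at night", ending no later than the morning of Day 7. Protocol 7.4.2 item 5 and SAP 10.1.4 list the timepoints the same way: three first-day readings, then morning and night by day.

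The time origin is set by Protocol 3.7.1.4: "the first application of IMP will be given at the trial site" once the baseline evaluations are finished. Its date and time are recorded, but no clock hour is prescribed.

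SAP 6.4 states that, for the VRS, "the timepoint will be determined based on the amount of time that has elapsed from the start of IMP administration". Table 6.4-2 gives 16 windows: Hour 4 (1 to <6), Hour 8 (6 to <10), Hour 12 (10 to <18), then every 12 h from Hour 24 to Hour 168, each from 6 h before to just under 6 h after its nominal time. For ties, "If multiple data exist within the allowable window of the timepoint, the data obtained last will be used for analyses".

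SAP 10.1.4 adds a second analysis by time of day, for which "Morning or evening will be determined based on the time label entered in the case report form (CRF"; it does not use Table 6.4-2. SAP 13.1 does not list elapsed-time binning as a change from the protocol.

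**The concern.** The diary runs on the clock, while the bins run on hours since a clinic visit. The two agree only if the first application falls at a suitable hour relative to the child's own diary times. Otherwise the same diary entry receives a different timepoint label depending on when the clinic visit ended.

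Three things are at stake in the main VRS tables. The last planned timepoint may be observed in only some of the children. Bins may mix morning and night itch across children; the planned split by time of day suggests the sponsor thinks the distinction may matter. In some cases a collected reading may be dropped by the last-in-window rule. VRS is not collected at ages 2-6, and at least 8 of the 60 subjects are to be of that age, so at most 52 children in three arms contribute if enrolment meets its target.

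**Working it through.** **Inputs.** Windows and tie rule: SAP 6.4. Reading schedule: Protocol 3.7.1.5 and 7.4.2 item 5, with Day 7 counted as days after the start, which matches a table ending at Hour 168. Let s be the clock time of the first application, m the usual morning reading and n the usual night reading. The documents give none of these three, so all values below are assumptions.

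**Elapsed times.** Morning of Day k: 24k + m - s. Night of Day k: 24k + n - s.

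**The table reproduced.** The plan has 3 + 6×2 + 1 = 16 readings and 16 windows. With s = 10:00, m = 07:00, n = 19:00, every window receives exactly one reading and the Day 7 morning (165 h) falls in Hour 168. The table fits a morning start.

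**When mornings move.** The Day k morning stays in Hour 24k only if 24k + m - s ≥ 24k - 6, that is s ≤ m + 6 h. Beyond that it falls one bin earlier: Day 1 morning in Hour 12, Day 7 morning in Hour 156. The limit is 12:00 for m = 06:00, 13:00 for 07:00 and 14:00 for 08:00.

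**When nights move.** The Day k night falls in Hour 24k once s > n - 6 h.

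**Example, s = 15:00, m = 07:00, n = 20:00.**

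| Reading | Elapsed (h) | Bin |
|---|---|---|
| Day 1 morning | 24 + 7 - 15 = 16 | Hour 12 |
| Day 1 night | 24 + 20 - 15 = 29 | Hour 24 |
| Day 2 morning | 48 + 7 - 15 = 40 | Hour 36 |
| Day 6 night | 144 + 20 - 15 = 149 | Hour 144 |
| Day 7 morning | 168 + 7 - 15 = 160 | Hour 156 |

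Hour 168 is empty and no diary pair shares a bin. A 12 h reading, if taken, would share Hour 12 with the Day 1 morning and be dropped.

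**Overwriting.** A night and the next morning share a bin only if m + 6 < s ≤ n - 6. This band is n - m - 12 hours long:

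- 07:00/19:00: none
- 07:00/20:00: 13:00 to 14:00
- 07:00/21:00: 13:00 to 15:00
- 07:00/22:00: 13:00 to 16:00

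Inside the band, at fixed clock times, all 6 pairs collide. The 6 night readings are dropped and Hours 24, 48, ..., 144 and 168 are empty. By the same arithmetic, if morning and night are less than 12 h apart, the same-day pair collides for n - 6 < s ≤ m + 6 and the morning reading is dropped. At exactly 12 h spacing neither band exists. With timing variation of SD 0.5 h at 07:00/19:00, the mean number of night-to-morning collisions is 1.52 of 6 for a start at 13:00 and 0.13 of 6 for a start at 14:00.

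**How many children (assumed m = 07:00).**

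- Starts uniform 09:00-17:00: (17 - 13)/(17 - 9) = 50% lack Hour 168.
- Same starts, share of filled Hour 24 values that are night readings: 4/8 = 50% for n = 19:00, 3/7 = 43% for 20:00, 2/6 = 33% for 21:00.
- Same starts, simulated with SD 0.5 h: about 3%, 5% and 10% of readings overwritten for n = 19:00, 20:00 and 21:00.
- Starts 09:00-12:00, SD 0.5 h: all these losses are close to zero.

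**The case against.** Elapsed time is a defensible scale for an early-onset endpoint: a reading at 160 h is nearer to 156 h than to 168 h, so the label is true to time on treatment. The last reading is not lost. It sits in Hour 156, and LOCF carries it to Hour 168. Protocol 3.2.1 sets applications about 12 h apart and VRS is read before application, so the overwriting band should be narrow or absent. A label-based analysis is already planned (CT-5.7.4 and CT-5.7.5). The percentages depend on clock hours the documents do not contain. The diary also stops at the Week 1 examination (±2 days), so late bins can be empty under any labelling. VRS is one of several secondary endpoints, with no significance level set.

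Most of this stands and limits the point. It does not remove it. The label-based analysis is additional and its listed tables include no LOCF version; the main MMRM, OC and LOCF tables (CT-5.7.1 to CT-5.7.3) still use the bins. The elapsed-time argument does not explain why the stated timepoints are diary mornings and nights, or why 16 readings fit 16 windows only for suitable start hours.

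**Conclusion.** The mismatch is real and worth correcting, but modest. It follows from the documents that a start more than 6 h after the usual morning reading relabels that child's diary mornings and leaves Hour 168 without an observed value. How often this happens cannot be determined from them: under the assumed hours above it ranges from about none to about half of the children.

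A reader might infer more than this:

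- **That every afternoon start loses Hour 168.** Not so: a 12:30 start with a 07:00 reading gives 168 + 7 - 12.5 = 162.5 h, inside the window.
- **That half of the night-and-morning pairs are generally overwritten.** Not so: it takes spacing other than 12 h, or timing variation, and a start in or near a narrow band. Inside the band at fixed times, one reading of each pair is dropped.
- **That the treatment comparison is biased.** Allocation is randomised and blinded, and nothing in the documents ties start hour to arm.

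If Day 7 instead meant Study Day 7 with the start as Day 1, Hours 156 and 168 would be empty even for a morning start, and start hour would not be the cause; the wording of Protocol 7.4.2 item 5 favours the count used here. The primary safety endpoint and the sample size are unaffected.

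**What to change.** In SAP 6.4 and 10.1.4:

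- Keep elapsed-time windows only for the first-day 4, 8 and 12 h readings, with the Hour 12 window closing before the next-morning diary entry.
- In the main VRS OC, LOCF and MMRM analyses, assign every later reading to Day k morning or Day k night from the CRF label, as the second analysis in 10.1.4 already does.
- End at the Day 7 morning, stating that days are counted after the start.
- Keep actual elapsed hours for time to response in VRS (SAP 10.1.9).
- Record the timepoint definition in SAP 13.1 if any difference from Protocol 7.4.2 remains.

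The 3 first-day readings and 13 diary readings then map one-to-one to 16 timepoints for any start hour, with no diary reading overwritten. The cost is SAP wording and programming; the label is already collected. The downside is that time since first application will vary by several hours between children within each label.

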6.5 Handling of Missing Values

Missing data for incidence of success in IGA will be handled as described in “[Section 6.3.1 Response in Investigator’s Global Assessment.](#)” Other variables at each timepoint will be analyzed based on the OC and LOCF data sets.

6.6 Significance Level and Confidence Coefficient

No significance tests will be used in this trial; therefore, no significance levels are set. The confidence coefficient is set at two-sided 95%.

6.6.1 Multiple Comparisons and Multiplicity

Multiplicity adjustment will not be conducted.

7 Disposition of Subjects

7.1 Disposition of Subjects

Data will be summarized for overall population and by age group (<7 or ≥ 7). The numbers of screened and randomized subjects will be provided. The following frequency distributions will be provided for overall population and by treatment group, unless otherwise specified. The frequency distribution (number and percentage relative to all subjects randomized) of subjects treated, those who completed the trial, and those who discontinued the trial will be calculated. For subjects who discontinue the trial, the frequency distribution will be calculated by reason for discontinuation.

7.2 Statistical Analysis Sets

Data will be summarized for overall population and by age group (<7 or ≥ 7). For the randomized subjects, the number and percentage of subjects included in the efficacy set, safety set, and pharmacokinetic analysis set will be provided.

7.3 Protocol Deviations

The number and percentage of subjects with major protocol deviations will be provided for overall population and by treatment group. The number and percentage of major protocol deviations occurring in each trial site will be provided for overall population and by treatment group.

8 Description of Analysis Datasets

8.1 Demographics and Baseline Characteristics

Data will be summarized for overall population and by age group (<7 or ≥ 7). For the randomized subjects, age, gender, duration of AD, body weight, height, BMI, race, baseline IGA score, and nation will be summarized for overall population and by treatment group using descriptive statistics or frequency distribution.

Affected BSA at baseline will be categorized as follows and summarized for overall population and by treatment group using frequency distribution.

Affected BSA categories: $\geq 5\%$ to $<10\%$, $\geq 10\%$ to $<30\%$, and $\geq 30\%$

8.2 Medical History/Complications

Medical history and complications will be coded by MedDRA/J system organ class (SOC) and preferred term (PT). The medical history and complications will be listed, but not summarized.

8.3 Prior and Concomitant Medications

For the randomized subjects, the numbers and percentages of subjects who take any concomitant medication before the start of IMP administration, during the assessment period, and after the last IMP administration will be provided by medication for the overall population and by treatment group. The medications will be coded using the WHO Drug Dictionary, and summarized by ATC Classification Level 2 and Preferred Name.

8.4 Concomitant Therapies

The concomitant therapies will be listed, but not summarized.

9 Safety Analysis

The following safety endpoints will be analyzed in the safety set (SS).

9.1 Primary Endpoint

The primary endpoint in this trial is the number and percentage of subjects experiencing adverse events (AEs). The analysis of AEs is described in [Section 9.3](#).

9.2 Exposure to the IMP (Number of Subjects, Duration, and Doses)

Treatment compliance with the amount of administration and the number of administrations, calculated as described in [Section 6.3.2](#), will be classified into the following categories, and the number and percentage of subjects will be provided for the overall population and by treatment group. The treatment compliance from baseline to Week 4 will be provided. The number and percentage of subjects who received IMP administration during each week (Week 1, Week 2, Week 3, Week 4, and every week thereafter, if necessary; Any Exposure) will be provided.

Categories of treatment compliance with the amount of administration and the number of administrations: <50%, ≥50% to <60%, ≥60% to <70%, ≥70% to <80%, ≥80% to <90%, ≥90% to <100%, ≥100% to <110%, ≥110% to <120%, ≥120%

9.3 Adverse Events

Data will be summarized for the overall population and by age group (<7 or ≥7). All AEs will be coded using the MedDRA/J SOC and PT.

The number and percentage of subjects experiencing the following treatment-emergent adverse events (TEAEs) will be provided for the overall population and by treatment group. Skin and subcutaneous tissue disorders will also be summarized by the grade in the Common Terminology Criteria for Adverse Events (CTCAE) v4.0 Japanese JCOG edition.

1. TEAEs
2. TEAEs resulting in death
3. Serious TEAEs
4. TEAEs leading to discontinuation of IMP administration
5. TEAEs by severity
6. TEAEs by CTCAE grade (only skin and subcutaneous tissue disorders)
7. TEAEs at treatment areas

For TEAEs and non-serious TEAEs reported in at least 5% of subjects in any treatment group, the number and percentage of subjects will be provided for the overall population and by treatment group.

9.4 Potentially Drug-related TEAEs

Potentially drug-related TEAEs (AEs for which a causal relationship with the IMP cannot be ruled out) will be summarized in the same manner as AEs. Serious potentially drug-related TEAEs will also be summarized.

9.5 Clinical Laboratory Tests

For laboratory parameters (except qualitative urinalysis), measured values and changes from baseline at each timepoint will be summarized for the overall population and by

treatment group using descriptive statistics. Shift tables (except qualitative urinalysis) will be created for predose and postdose values classified into normal, high, or low based on the reference range by treatment group. For qualitative urinalysis, shift tables will be created for predose and postdose values by each parameter. The number and percentage of potential Hy's Law Cases will be provided for the overall population and by treatment group. A listing of the potential Hy's Law Cases will be provided. Potential Hy's Law Cases will be defined as follows:

Potential Hy's Law Cases are defined as subjects with AST or ALT ≥ 3 times the upper normal limit or whose levels increase ≥ 3 times the initial screening value, and with an increase in total bilirubin level ≥ 2 times the upper normal limit or initial screening value.

9.6 Vital Signs (Including Body Weight)

Measured values and changes from baseline in body weight, body temperature, blood pressure (systolic/diastolic), and pulse rate at each timepoint will be summarized for the overall population and by treatment group using descriptive statistics. For body temperature, blood pressure (systolic/diastolic), and pulse rate, the number and percentage of subjects with potentially clinically significant vital sign abnormalities (Table 16.1-1) will be computed for the overall population and by treatment group. A listing of subjects with potentially clinically significant abnormalities will be provided.

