In an 8-week repeated-dose percutaneous toxicity study in juvenile rats (25 days old at the start of administration), white petrolatum 0% (vehicle), OPA-15406 ointment 0.3% (male: 3.76 mg/kg, female: 4.23 mg/kg), 1% (male: 12.56 mg/kg, female: 14.32 mg/kg), or 3% (male: 38.52 mg/kg, female: 43.83 mg/kg) was administered once daily to intact skin (open cutaneous) approximately equivalent to 10% of total BSA. As a result, no changes associated with the test substance were observed on the administration sites in any of the treatment groups. Although suppressed weight increase and reductions in food intake and grip strength were observed in female rats with 1% or 3% ointment, these changes were not developmental toxicity and they resolved with washout. Also, there was no difference in the toxicity threshold between adult and juvenile rats. As the profile of OPA-15406 is such that it reaches the central nervous system (CNS) and the brain is known to develop after birth, a 10-week repeated-dose percutaneous toxicity study was conducted in neonatal rats (4 days old at the start of administration) with a focus on CNS development, but no influence of OPA-15406 on the function or structure of the CNS was found.

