### **3.3 Trial Population**

#### **3.3.1 Number of Subjects and Description of Population**

The target population of this trial is pediatric patients with AD with an IGA score of 2 (mild) or 3 (moderate). Subjects will be included in the trial to reach the target number of 60 subjects for IMP administration (at least 8 subjects aged 2 to 6 years old). Any withdrawals will not be supplemented.

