13.1	Changes From the Efficacy Analyses Planned in the Protocol	24
13.2	Changes From the Pharmacokinetic Analyses Planned in the Protocol	24
14	References	25
15	Revision History	26
16	Appendix	27
16.1	Criteria for Potentially Clinically Significant.....	27
16.2	Table of Contents.....	28

List of Abbreviations and Definition of Terms

List of Abbreviations

Abbreviation	Expansion
AD	Atopic Dermatitis
BSA	Body Surface Area
EASI	Eczema Area and Severity Index
IGA	Investigator's Global Assessment
IMP	Investigational Medicinal Product
LOCF	Last Observation Carried Forward
MedDRA	Medical Dictionary for Regulatory Activities
MMRM	Mixed Model Repeated Measures
OC	Observed Cases
POEM	Patient-Oriented Eczema Measure
QTcB	QT interval as correlated by Bazett's formula
QTcF	QT interval as correlated by Fridericia's formula
SS	Safety Set
TEAE	Treatment-emergent Adverse Event
VAS	Visual Analogue Scale
VRS	Verbal Rating Scale

Definition of Terms

Term	Definition
Descriptive statistics	Number of subjects, mean, standard deviation, minimum, median, and maximum
Descriptive statistics of plasma OPA-15406 concentrations	Number of subjects, arithmetic mean, coefficient of variation, standard deviation, minimum, median, and maximum
Frequency distribution	Number and percentage of subjects

1 Introduction

This statistical analysis plan (SAP) documents the detailed methodology of summarization/analyses and evaluation to provide the trial data required for the preparation of a clinical study report of Trial 271-102-00002. This document has been created based on Protocol No. 271-102-00002, Version 2.0, issued on 14 Nov 2016. The pharmacokinetic analyses are detailed in [Section 11](#).

2 Trial Objectives

Primary Objective: To evaluate the safety of 0.3% and 1% OPA-15406 when applied twice daily for 4 weeks in pediatric patients with atopic dermatitis (AD)

Secondary Objective: To evaluate the efficacy (dose response) and pharmacokinetics of 0.3% and 1% OPA-15406 when applied twice daily for 4 weeks in pediatric patients with AD

3 Trial Design

This is a multicenter, randomized, double-blind, vehicle-controlled, parallel-group comparison trial to evaluate the safety, efficacy, and pharmacokinetics of OPA-15406 ointment in pediatric patients with AD. This trial consists of the 0.3% OPA-15406 group, the 1% OPA-15406 group, and the vehicle group. The trial design is shown in Figure 3-1.

1) Screening period

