16.1 Criteria for Potentially Clinically Significant

Table 16.1-1 Criteria for Potentially Clinically Significant Vital Sign Abnormalities		
TEST	CRITERIA 1	CRITERIA 2
DIASTOLIC BLOOD PRESSURE (MMHG)	DIASTOLIC BLOOD PRESSURE (mmHg) < 50 AND DECREASE \geq 15	DIASTOLIC BLOOD PRESSURE (mmHg) > 105 AND INCREASE \geq 15
HEART RATE (BEATS/MIN)	HEART RATE (BPM) < 50 AND DECREASE \geq 15	HEART RATE (BPM) > 120 AND INCREASE \geq 15
SYSTOLIC BLOOD PRESSURE (MMHG)	SYSTOLIC BLOOD PRESSURE (mmHg) < 90 AND DECREASE \geq 20	SYSTOLIC BLOOD PRESSURE (mmHg) > 180 AND INCREASE \geq 20
TEMPERATURE (°C)	-	TEMPERATURE (°C) \geq 37.8 AND INCREASE \geq 1.1°C
WEIGHT (KG)	WEIGHT (kg) DECREASE \geq 7%	WEIGHT (kg) INCREASE \geq 7%

Table 16.1-2 Criteria for Potentially Clinically Significant ECG Abnormalities		
CLASSIFICATION	CATEGORY	CRITERIA
VENT RATE OUTLIERS	NOTABLE INCREASES	25% INCREASE FROM BASELINE AND VENTRICULAR RATE > 100 BPM
VENT RATE OUTLIERS	NOTABLE DECREASES	25% DECREASE FROM BASELINE AND VENTRICULAR RATE < 50 BPM
PR OUTLIERS	NOTABLE CHANGES	\geq 25% CHANGE FROM BASELINE WHEN PR > 200 MSEC
QRS OUTLIERS	NOTABLE CHANGES	\geq 25% CHANGE FROM BASELINE WHEN QRS > 100 MSEC
QT	NEW ONSET (\geq 450 MSEC)	NEW ONSET (\geq 450 MSEC) IN QT MEANS A SUBJECT WHO ATTAINS A VALUE \geq 450 MSEC DURING TREATMENT PERIOD BUT NOT AT EACH BASELINE
QTcB	NEW ONSET (\geq 450 MSEC) IN MALE OR (\geq 470 MSEC) IN FEMALE	NEW ONSET (\geq 450 MSEC IN MALE OR \geq 470 MSEC IN FEMALE) IN QTcB MEANS A SUBJECT WHO ATTAINS A VALUE \geq 450 OR \geq 470 MSEC DURING TREATMENT PERIOD BUT NOT AT EACH BASELINE
QTcB	NEW ONSET (\geq 450 MSEC) AND \geq 10% INCREASE	NEW ONSET (\geq 450 MSEC) AND \geq 10% INCREASE IN QTcB MEANS A SUBJECT WHO ATTAINS A VALUE \geq 450 MSEC AND \geq 10% INCREASE DURING TREATMENT PERIOD BUT NOT AT EACH BASELINE
QTcB	INCREASE 30 - 60 MSEC	INCREASE IN CHANGE FROM BASELINE VALUE \geq 30 AND \leq 60 MSEC
QTcB	INCREASE > 60 MSEC	INCREASE IN CHANGE FROM BASELINE VALUE > 60 MSEC

Table 16.1-2 Criteria for Potentially Clinically Significant ECG Abnormalities		
CLASSIFICATION	CATEGORY	CRITERIA
QTcF	NEW ONSET (≥ 450 MSEC) IN MALE OR (≥ 470 MSEC) IN FEMALE	NEW ONSET (≥ 450 MSEC IN MALE OR ≥ 470 MSEC IN FEMALE) IN QTcB MEANS A SUBJECT WHO ATTAINS A VALUE ≥ 450 OR ≥ 470 MSEC DURING TREATMENT PERIOD BUT NOT AT EACH BASELINE

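### Body weight is summarised only as raw-kg statistics pooled over ages 2 to 14, so a proportional loss or suppressed gain in the few children under 7 can be diluted

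*SAP*

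**What the plan says.** Protocol Table 3.7-1 has body weight measured at screening, baseline and Weeks 1, 2 and 4 (or withdrawal). SAP 9.6 then states: "Measured values and changes from baseline in body weight, body temperature, blood pressure (systolic/diastolic), and pulse rate at each timepoint will be summarized". It does so with descriptive statistics, per arm and with all arms combined. The SAP's definition of terms gives these statistics as "Number of subjects, mean, standard deviation, minimum, median, and maximum". Protocol 7.6.3 plans the same kind of summary for vital signs. Neither document plans percent change in weight or a weight summary by age.

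Both tools are used elsewhere in the SAP:

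- **Age split at 7.** Disposition (7.1), analysis sets (7.2), demographics (8.1), adverse events (9.3, "Data will be summarized for the overall population and by age group (<7 or ≥7") and the IGA subgroup analysis (10.4).
- **Percent change.** EASI, VAS and POEM (10.1.7).
- **A proportional weight criterion.** Table 16.1-1 flags a decrease or an increase of 7% or more.

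The sentence in 9.6 that orders the count of flagged subjects does not name weight: "For body temperature, blood pressure (systolic/diastolic), and pulse rate, the number and percentage of subjects with potentially clinically significant vital sign abnormalities". The sentence after it plans a listing of flagged subjects and does not exclude weight. The titles CT-11.2 (listing), CT-11.3 (incidence) and CT-11.4 (criteria) do not settle whether weight is included.

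Protocol 3.3.1 requires "at least 8 subjects aged 2 to 6 years old" out of 60.

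**The concern.** Weight is the safety measure that links most directly to the nonclinical findings. Protocol 1.1 reports of the juvenile study: "Although suppressed weight increase and reductions in food intake and grip strength were observed in female rats with 1% or 3% ointment". The same section reports reduced body weight and/or food consumption in the 4-week adult rat study and suppressed weight gain at 3% in the 13-week study. Safety is the primary objective, and protocol 1.3 shows that no AD patient treated so far was younger than 10.

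A kilogram is not the same signal at 12 kg as at 45 kg. When children of such different sizes are pooled, the mean gives a small child's proportional loss little weight, and the median is set by the older majority. If the under-7 children in one arm lost weight, or failed to gain it, the planned table could look unremarkable. No planned summary would show weight in that group by arm.

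**Working it through.** The plan states no figure for weight, so there is nothing of its own to reproduce. The documents give no body weights or growth rates; those below are assumptions.

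**Inputs from the documents.** 20 subjects per arm (SAP 12.2). A floor of 8 aged 2 to 6 in 60, so 8/3 = 2.7 per arm on average. The floor applies to the whole trial. Protocol 3.6 leaves the minimization details to a separate specification, so balance by age across arms is not confirmed. The weight criterion is 7% (Table 16.1-1).

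**Scale.** 7% is 0.07 × 12 = 0.84 kg at 12 kg and 0.07 × 45 = 3.15 kg at 45 kg. Conversely, a fall of 0.84 kg at 45 kg is 0.84/45 = 1.9%.

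**Dilution.** Let k children under 7 weigh 16 kg and each lose a fraction f. Let the other 20 − k weigh 35 kg and each gain 0.2 kg, which is 0.2/35 = 0.571%.

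Mean kg change = [k × (−16f) + (20 − k) × 0.2]/20

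Mean percent change = [k × (−100f) + (20 − k) × 0.571]/20

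| k | f | Pooled mean, kg | Pooled mean, % | Under-7 row, % |
|---|---|---|---|---|
| 3 | 7% | (−3.36 + 3.40)/20 = +0.002 | (−21 + 9.71)/20 = −0.56 | −7 |
| 3 | 5% | (−2.40 + 3.40)/20 = +0.05 | (−15 + 9.71)/20 = −0.26 | −5 |
| 6 | 5% | (−4.80 + 2.80)/20 = −0.10 | (−30 + 8.00)/20 = −1.1 | −5 |

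In the first row the rest of the planned statistics would be median +0.20 kg, minimum −1.12 kg and SD about 0.48 kg. Percent change pooled over age is nearly as uninformative as kilograms; it is the age split that reveals the loss.

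**Sensitivity.** With k = 3, f = 7%, young children at 14 kg and older ones at 32 kg gaining 0.3 kg, the pooled mean is (3 × −0.98 + 17 × 0.3)/20 = +0.11 kg, or −0.25% as percent change. Let young weight run from 12 to 18 kg, older weight from 25 to 45 kg and older gain from 0 to 0.5 kg:

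- k = 3: pooled mean −0.19 to +0.30 kg; pooled percent mean −1.05% to +0.65%.
- k = 8: pooled mean −0.50 to −0.04 kg, so always negative.

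**Suppressed gain.** Return to k = 3 and let the young children stay level while the other 17 gain 0.2 kg. The arm mean is 17 × 0.2/20 = +0.17 kg, the median is +0.20 kg and the minimum is 0. If every vehicle child gains 0.2 kg, the vehicle mean is +0.20 kg, a gap of 0.03 kg. No child reaches the 7% criterion.

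**The case against.** The strongest reply is that the planned table is more than a mean. It gives minimum, median and maximum, and in the 7% case a minimum of −1.12 kg beside a median of +0.20 kg should catch the eye. There is also a vehicle arm: if all its children gain 0.2 kg, the treated arm falls short by 0.20 − 0.002 = 0.198 kg. Children losing 7% meet the Table 16.1-1 criterion and should appear in the listing if weight is included there. Individual vital signs are in PDATA-7, and weight loss reported as an adverse event enters tables already split at age 7. Laboratory tests and ECGs are not split by age either.

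Most of this stands, and it rules out three stronger readings that a reader might infer:

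- **That weight is reported only as a mean, or that a loss would be invisible outside listings.** The SAP's definition of descriptive statistics and the age-split adverse event tables contradict this.
- **That dilution will occur.** It depends on assumed weights, growth and numbers; 8 is a floor, and with more young children the pooled mean turns negative.
- **That the youngest are known to be at greater risk.** Protocol 1.1 and 2.1 report no lower toxicity threshold in juvenile rats and recovery after washout. The protocol 3.2.1 formula does give more ointment per kg to a smaller child. With 1% ointment on 40% of BSA twice daily, 12 kg and 87 cm gives BSA √(87 × 12/3600) = 0.5385 m² and 0.5385 × 0.4 × 10 × 10 mg × 2/12 = 3.59 mg/kg/day. At 50 kg and 163 cm the figure is 1.5046 × 0.4 × 10 × 10 mg × 2/50 = 2.41. These are applied amounts at assumed sizes and show neither absorption nor a weight effect.

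The safeguards are nevertheless partial. The minimum is one value without age or body size, and an older child's modest fluctuation can set it. The median follows the majority. The vehicle comparison remains pooled over age. The 7% flag misses a uniform 5% loss and any suppressed gain, and 9.6 does not name weight in the count.

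**Conclusion.** The point holds as a cheap improvement, not as a flaw that invalidates the safety analysis. SAP 9.6 summarises weight on a scale and over an age range that suit neither its own proportional criterion nor its own age grouping elsewhere. With about three under-7 children per arm, a 5% to 7% loss in all of them can leave the pooled mean near zero or positive (+0.002 to +0.05 kg in the table's assumptions, −0.19 to +0.30 kg for a 7% loss over the wider range). With six or eight the mean falls below zero in the cases worked here. All these figures rest on assumed weights, growth and losses. Separately, and without any assumption, the count sentence in 9.6 and Table 16.1-1 disagree on whether weight is included.

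**What to change.** In SAP 9.6 and output CT-11.1, add percent change from baseline in body weight at Weeks 1, 2 and 4, by treatment group within the existing age groups (<7, ≥7), beside the kilogram summary. Show individual percent changes for the under-7 children by arm. Adding percent change without the age split would not be enough.

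In the same edit, reconcile the 9.6 count sentence with Table 16.1-1, and state whether CT-11.2 and CT-11.3 cover weight.

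The cost is a few lines of SAP text and one extra table block, from data already collected. The under-7 rows will hold few children and should be labelled descriptive only.
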